Weill Cornell Medical College

A Phase II Trial of the Aurora Kinase A Inhibitor MLN8237 in Patients with Metastatic Castrate Resistant and Neuroendocrine Prostate Cancer

Study Chair:

[name]

Div of Hematology & Medical Oncology
New York Presbyterian – Weill Cornell Medical College
[name]
New York, NY 10065
[contact]
[contact]
[contact]

This is an investigator-initiated study. The principal investigator [name], who may also sometimes be referred to as the sponsor-investigator, is conducting the study and acting as the sponsor. Therefore, the legal/ethical obligations of the principal investigator include both those of a sponsor and those of an investigator.

WCMC Co-Investigators:

[name]
[name]
[name], NP
[name], PA

Statistician:

[name], Dr.PH
Weill Cornell Medical College
Division of Biostatistics and Epidemiology
[contact]

WCMC Collaborating-Investigators:

[name]
Weill Cornell Medical College
Department of Pathology
[name]
New York, NY 10065
[contact]
[contact]
[contact]

Coordinating Data Manager:

[name]
Weill Cornell Medical College
New York, NY 10021
[contact]
[contact]
[contact]

Coordinating Regulatory Manager:

[name]
Weill Cornell Medical College
[name]
[contact]
[contact]
[contact]

INVESTIGATOR AGREEMENT

I have read the protocol entitled “A Phase II Trial of the Aurora Kinase A Inhibitor MLN8237 in Patients with Metastatic Castrate Resistant and Neuroendocrine Prostate Cancer”, version 2, dated May 14, 2014.

I agree to conduct the study as detailed herein and in compliance with ICH Guidelines for Good Clinical Practice and applicable regulatory requirements and to inform all who assist me in the conduct of this study of their responsibilities and obligations.

Principal investigator printed name

Principal investigator signature

Date

Investigational site or name of institution and location (printed)

Protocol summary

WCMC IRB Protocol Number: 1210013164
Title of Study: A Phase II Trial of the Aurora Kinase A Inhibitor MLN8237 in Patients with Metastatic Castrate Resistant and Neuroendocrine Prostate Cancer
Study Chair: [name]
Study Center(s): WCMC and up to 10 additional sites
Number of Patients: 60 (multi-institutional, estimated accrual 3 per month, duration of enrollment - 24 months)
Concept and Rationale: The amount of neuroendocrine differentiation increases in late stages of prostate cancer and after exposure to androgen deprivation therapy, and contributes to the development of castrate resistance. Transformation to a predominantly androgen receptor (AR)- negative, neuroendocrine phenotype occurs in approximately 25% of late stage prostate cancer; these have been termed neuroendocrine or anaplastic prostate cancer. As more potent anti-androgen therapies are being introduced into the clinical arena, it is predicted that the incidence of neuroendocrine prostate cancer (NEPC) will escalate. There is currently no proven effective therapy for NEPC, and most patients survive less than one year. Aurora kinase A (AURKA) and N-myc (MYCN) are significantly overexpressed and amplified in NEPC compared to prostate adenocarcinoma, and these proteins cooperate to directly induce neuroendocrine differentiation ([name] et al, Cancer Discovery 2011). In preclinical models, aurora kinase inhibition resulted in dramatic and preferential anti-tumor activity in NEPC with suppression of neuroendocrine marker expression. MLN8237 is an orally administered Aurora kinase A inhibitor that has demonstrated broad antitumor activity in vitro and in vivo, and the RP2D as monotherapy in adults with refractory solid tumors was 50 mg BID for 7 days in 21-day cycles.
Primary Objective(s): The primary endpoint is the proportion of patients who are free from radiographic progression 6 months following initiation of treatment with MLN8237.
Secondary Objective(s): To determine the radiologic response rate, overall survival (OS), radiographic progression free survival (rPFS), PSA response rate, circulating tumor cell (CTC) response, and serum neuroendocrine markers in response to therapy.
Exploratory objectives: To evaluate molecular biomarkers archival and metastatic tissue, including IHC and FISH for Aurora kinase A and N-myc overexpression and amplification, neuroendocrine markers, AR status, ERG fusion, and other genomic mutations determined by sequencing. To evaluate plasma DNA for AURKA and MYCN amplification.
Primary Endpoint(s): Radiographic progression is measured using modified RECIST 1.1 criteria.
Secondary Endpoint(s): Overall Survival is defined as time from first treatment until death. rPFS will be defined as the time from first treatment day until objective or symptomatic radiologic progression. Progression will be determined by RECIST 1.1 and bone progression is per PCWG2 criteria. PSA progression will be evaluated but will not be considered PD; PSA progression is defined as increase in PSA value of $\geq 25\%$ and an absolute increase of ≥ 2 ng/mL over baseline or nadir. Serum chromogranin A and neuron specific enolase response is defined as obtaining $>50\%$ reduction from baseline. CTC enumeration counts will be classified into favorable (≤ 5) or unfavorable (>5); baseline and post-cycle 2 classification will be compared. In addition, % changes in counts will be assessed. Molecular analysis will be performed on pre-treatment tissue specimens and

plasma DNA.

Study Design:

This is a multi-institutional single-arm, open-label Phase 2 trial evaluating MLN8237 in patients with histologically confirmed or clinically suspected metastatic neuroendocrine prostate cancer (see inclusion criteria for full list of eligibility). All subjects will have a mandatory metastatic tumor biopsy at time of enrollment for research purposes. Subjects will be treated with MLN8237 at 50 mg twice daily for 7 days repeated every 21 days. Individual dose reductions will be made on the basis of the AEs observed. Therapy will continue until disease progression, unacceptable toxicity as a result of MLN8237, or withdrawal of patient consent. Patients will be followed with history, physical, and blood tests at each visit to monitor for toxicity. Response and progression will be evaluated by CT/MRI scan and bone scan after every 3 cycles and determined using RECIST v1.1. PSA and investigational tumor markers (assessed centrally) will be followed every cycle. CTC counts by CellSearch will be performed at baseline, at 4-6 weeks, and upon progression. Patients will be followed for survival endpoints following completion of this study until death.

Main Criteria for Inclusion/Exclusion (summary):

- 1) Metastatic prostate carcinoma and at least one of the following:
 - a) Histologic diagnosis of small cell or neuroendocrine prostate cancer
 - b) Histologic diagnosis of prostate adenocarcinoma plus $\geq 50\%$ immunohistochemical staining for neuroendocrine markers (such as chromogranin, synaptophysin or neuron specific enolase)
 - c) Development of liver metastases in the absence of PSA progression as defined by Prostate Cancer Working Group 2 (PCWG2) criteria.
 - d) Serum chromogranin A level $>5 \times$ upper limit of normal and/or serum neuron specific enolase (NSE) $>2 \times$ upper limit of normal
- 2) Patients with pure small cell neuroendocrine carcinoma on histology are not required to have received prior androgen deprivation therapy (ADT) or castrate levels of testosterone. Other patients are required to have surgical or ongoing chemical castration, with baseline testosterone level $<50\text{ng/dL}$.
- 3) ECOG performance status 0-2
- 4) Willing and able to give informed consent
- 5) Estimated life expectancy $>3\text{months}$

Key Exclusion criteria:

- 1) Active serious comorbid illness which in investigator's opinion will preclude completion of this study or interfere with determination of causality of any adverse effects experienced in this study
- 2) Absolute neutrophil count $<1,500/\text{mm}^3$
- 3) Platelet count $<100/\text{mm}^3$
- 4) Hemoglobin $<9.0\text{ g/dL}$
- 5) Total bilirubin $>\text{ULN}$, SGOT (AST) and SGPT (ALT) $>1.5 \times \text{ULN}$. AST and/or ALT may be up to 5X ULN if with known liver metastases.
- 6) inadequate renal function as defined by creatinine $>1.5 \times \text{ULN}$. If creatinine $>1.5\text{ ULN}$, calculated creatinine clearance must be $\geq 40\text{ mL/minute}$ (Cockcroft-Gault)
- 7) Patient has received other investigational drugs with 14 days before treatment

Intervention and Mode of Delivery:

Subjects will be treated with MLN8237 at 50 mg twice daily for 7 days repeated every 21 days

Duration of Intervention and Evaluation:

MLN8237 for CRPC and NEPC

IRB : 1210013164

Version 2: May 14, 2014

Patients will continue therapy until disease progression or unacceptable toxicity as a result of MLN8237. Patients will be followed with history, physical, and blood tests at each visit to monitor for toxicity. Response and progression will be evaluated by CT/MRI scan and bone scan every 3 cycles and determined using RECIST v1.1. PSA and serum chromogranin A and NSE will be followed every cycle. CTC counts will be performed at baseline, at 4-6 weeks, and upon progression. Patients will be followed for survival endpoints following completion of this study until death.

Statistical Methods:

The primary endpoint is the proportion of patients who are free from radiographic progression at 6 months, following treatment with MLN8237. Based on the phase II trial by Meulenbeld et al (BJUI 2012), the proposed null hypothesis (H_0) is that $\leq 15\%$ of patients will be radiographic progression-free at 6 months and the alternative hypothesis (H_a) is that $\geq 30\%$ of patients will be radiographic progression-free at 6 months.

Sample size recommendations for the phase II design are determined according to Ahern's exact single-stage phase II design (A'Hern RP, 2001). We project a 6-month radiographic progression-free proportion of 15%, below which the response will be unacceptable, and a 6-month radiographic progression-free proportion of 30%, above which the regimen will be considered worthy of further exploration. The null hypothesis that the 6-month radiographic progression-free proportion is less than or equal to 15% will be tested against the alternative hypothesis that the 6-month radiographic progression-free proportion is greater than or equal to 30%.

The sample size computations were performed assuming a 5% level of significance and 80% power. A total of 48 patients will be required to enroll in the study. The treatment will be declared effective and worthy of further testing if 12 or more patients are free from radiographic progression at 6 months among the 48 patients entered into the study. This exact single-stage design yields a ≥ 0.80 probability of a positive result if the true percentage of patients who are free from radiographic progression at 6 months is $\geq 30\%$. It yields a ≥ 0.95 probability of a negative result if the true percentage of patients who are free from radiographic progression at 6 months is $\leq 15\%$. Assuming 10-20% of patients will be unevaluable/ineligible, we anticipate that a total 60 patients will be enrolled in the study.

Approximately 20% of patients are expected to have histologic entry criteria. With a sample size of approximately 12 patients meeting such criteria (i.e., 20% of 60 enrolled patients), a 95% confidence interval for the 6-month radiographic progression-free proportion in this subgroup of 12 patients can be expected to be within $\pm 25.9\%$ of the true 6-month radiographic progression-free proportion in this subgroup. This calculation assumes a 6-month radiographic progression-free proportion of 30% in patients with biopsy positive NEPC. This calculation is for descriptive/exploratory purposes only, with the intent of estimating the 6-month radiographic progression-free proportion among the small subgroup of patients with biopsy positive NEPC.

Analysis Plan for Endpoints:

Primary Endpoint:

The primary endpoint of 6-month radiographic progression-free proportion will be estimated and a 95% confidence interval will be estimated via binomial proportions.

Secondary Clinical Endpoints:

With adequate follow-up time, secondary endpoints of response rate and overall survival (OS) will be assessed. Radiologic response rate will be estimated and a 95% confidence interval will be estimated via binomial proportions. For OS and rPFS, Kaplan-Meier survival analysis and 95% confidence intervals will be calculated using Greenwood's formulae.

The frequency of subjects experiencing toxicities will be tabulated. Toxicities will be assessed and graded according to CTCAE v. 4.0 terminology. Exact 95% confidence intervals around the toxicity proportions will be calculated to assess the precision of the obtained estimates.

Exploratory objectives/correlative studies will be evaluated using descriptive statistics, graphical methods, and statistical modeling, as appropriate, to explore the relationship between response and Aurora -A and N-myc overexpression and/or amplification in circulating tumor cells or archival tissue.

Funding, Regulatory, and Feasibility Issues:

Study drug will be provided by Millennium Pharmaceuticals. A research grant from Millennium Pharmaceuticals to WCMC will be used to fund start up costs and per-subject reimbursement for additional sites (i.e. additional sites will be funded through WCMC). Correlative studies will be supplemented with funding from other grants of the investigators, including the Prostate Cancer Foundation, Damon Runyon Cancer Research Foundation, and the United States Department of Defense.

Patient Acceptability/Ethics and Consent Issues:

The patients eligible for this study have an aggressive subtype of prostate cancer that is currently incurable with a poor prognosis of less than 1 year. There is currently no standard treatment. Based on extensive preclinical data, there is strong biologic rationale for this study. MLN8237 is orally given and conveniently administered for patients. The study will be conducted in accordance with ethical principles founded in the Declaration of Helsinki. The IRB/IEC will review all appropriate study documentation to safeguard the rights, safety, and well-being of the patients. After the study has been fully explained, written informed consent will be obtained from either the patient or his/her guardian or legal representative before study participation.

	Screening	C1D1	C1D2-7	C1D8*	C1D15*	C_D1*	C_D2-7	C_D8*	After every 3 cycles	Progression	End of Study ¹²
Informed Consent	X										
ECG	X										
Medical History	X ¹	X		X	X	X		X		X	X
Physical Exam	X	X		X	X	X		X		X	X
Performance Status	X	X		X	X	X		X		X	X
Vital Signs²	X	X		X	X	X		X		X	X
CBC³	X	X		X	X	X		X		X	X
Chemistries⁴	X	X		X	X	X		X		X	X
PSA	X	X				X				X	X
Testosterone	X									X	X
CTC count⁵		X				X				X	X
Serum CgA, NSE⁶	X	X				X				X	X
Serum CEA⁷		X							X	X	X
blood for research⁸		X		X						X	X
CT/MRI⁹	X								X ⁹	X	X
Bone scan	X								X	x	X
Archival Tissue	X										
Metastatic Biopsy¹⁰	X									(Optional)	
MLN8237		X	X ¹¹				X				
Adverse Event Monitoring		X	X	X	X	X	X	X		X	X
Concurrent Medications	X	X		X	X	X		X		X	X

* Window for study visits is +/- 3 days

1 Comprehensive history required for enrollment; interval history satisfactory for subsequent visits

2 Vital signs must include temperature, blood pressure, heart rate, respiratory rate, weight and height at least once during screening (prior to C1D1); subsequent vitals must include at least blood pressure, heart rate, respiratory rate, and weight

3 CBC must include differential for WBC; CBC may be performed in any CLIA certified laboratory up to 3 days prior to chemotherapy administration

4 Chemistry may be performed at any CLIA certified laboratory up to 3 days prior to chemotherapy administration and must include electrolytes, AST, ALT, total bilirubin, alkaline phosphatase; D1 chemistry for all cycles must also include uric acid and LDH; C1D8 labs must also include uric acid and LDH

5 CTC counts are encouraged, but are not mandatory and must be performed via CellSearch methodology at the following time points: prior to chemotherapy C1D1 (or within one month prior to treatment), C3D1, and at progression or end of study.

6 Serum chromogranin and neuron specific enolase should be performed locally during screening, then centrally Day 1 of each cycle and at progression

7 Serum carcinoembryonic acid (CEA) level is performed centrally C1D1, after every 3 cycles (at time of scans), and at progression

8 Blood for research will be collected at the following time points: C1D1, C1D8, and at progression or end of study. On C1D1 sample, PBMC and plasma will be isolated separately. At other time points, plasma will be collected.

9 CT/MRI of abdomen/pelvis plus CT of chest; imaging modality should remain constant for the duration of the study (i.e. if baseline scan was MRI, follow up scans should be MRI). See section 7.0 for details

10 Biopsy of metastatic tumor can be performed at any time after informed consent prior to C1D1

11 MLN8237 will be given D1-7 of every cycle

12 Must occur >30 days from last dose of MLN8237; research lab procedures performed as part of progression visit do not need to be repeated

TABLE OF CONTENTS

	Page
PROTOCOL SUMMARY	4
STUDY CALANDER	8
1. BACKGROUND	12
1.1 Neuroendocrine Prostate Cancer	12
1.2 Aurora Kinase A and Prostate Cancer	13
1.3 MLN8237	15
1.4 Correlative Studies Background	23
2. OBJECTIVES	24
2.1 Primary Objectives	24
2.2 Secondary Objectives	25
2.3 Exploratory Objectives	25
3. STUDY DESIGN	25
4. SUBJECTS	26
4.1 Recruitment	26
4.2 Number of Patients	26
4.3 Inclusion Criteria	26
4.4 Exclusion Criteria	27
4.5 Registration Procedure	29
4.6 Duration of Follow-up	29
5. PATIENT EVALUATION	29
5.1 Screening Period	29
5.2 Treatment Period	30
6. CORRELATIVE STUDIES	35
6.1 CTC by Cellsearch	35
6.2 Plasma for research	35
6.3 Serum Tumor Markers	35
6.4 Archival tissue	35
6.5 Metastatic Tumor Biopsy	35
7. RADIOLOGIC EVALUATION	35
8. TREATMENT PLAN	36
8.1 Administration of MLN8237	36
8.2 Dose Modifications/ Delays	36
8.3 Packaging and Labeling	39
8.4 Excluded Medications and Procedures	39
8.5 Permitted Medications and Procedures	39

8.6	Precautions and Restrictions	40
8.7	Management of Clinical Events	41
8.8	Treatment Compliance	42
8.9	Duration of Treatment	42
8.10	Termination of Treatment and/or Study Participation	43
9.	STUDY DRUG ADMINISTRATION	43
9.1	Description of MLN8237	43
9.2	Preparation and Dispensation	44

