2.2 Secondary objectives

- To determine the overall survival with MLN8237
- To evaluate the objective response rate
- To determine the progression free survival with MLN8237
- To determine the PSA response rate with MLN8237
- To determine baseline and changes in circulating tumor cell count in response to therapy and at disease progression
- To determine serum neuroendocrine marker response with MLN8237

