- Withdrawal of patient consent
- Noncompliance with protocol-specified procedures which in the opinion of the investigator will expose subjects to undue risk or will significantly effect interpretation of study results

12. Statistical Considerations.

12.1. Sample Size Justification:

The primary endpoint is the proportion of patients who are free from radiographic progression at 6 months following treatment with MLN8237. Based on the phase II trial by Meulenbeld et al (BJUI 2012), the proposed null hypothesis (H_0) is that $\leq 15\%$ of patients will be radiographic progression-free at 6 months and the alternative hypothesis (H_a) is that $\geq 30\%$ of patients will be radiographic progression-free at 6 months.

Sample size recommendations for the phase II design are determined according to Ahern's exact single-stage phase II design (A'Hern RP, 2001). We project a 6-month radiographic progression-free proportion of 15%, below which the response will be unacceptable, and a 6-month radiographic progression-free proportion of 30%, above which the regimen will be considered worthy of further exploration. The null hypothesis that the 6-month radiographic progression-free proportion is less than or equal to 15% will be tested against the alternative hypothesis that the 6-month radiographic progression-free proportion is greater than or equal to 30%.

The sample size computations were performed assuming a 5% level of significance and 80% power. A total of 48 patients will be required to enroll in the study. The treatment will be declared effective and worthy of further testing if 12 or more patients are free from radiographic progression at 6 months among the 48 patients entered into the study. This exact single-stage design yields a ≥ 0.80 probability of a positive result if the true percentage of patients who are free from radiographic progression at 6 months is $\geq 30\%$. It yields a ≥ 0.95 probability of a negative result if the true percentage of patients who are free from radiographic progression at 6 months is $\leq 15\%$. Assuming 10-20% of patients will be unevaluable/ineligible, we anticipate that a total 60 patients will be enrolled in the study.

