12.3. Measurement of Effect

Progressive standard prostate cancer is often manifest by rising PSA levels, new lesions on bone scan, new disease-related symptoms and increasing size of a measurable soft tissue mass. Response is commonly assessed either biochemically (PSA change) or by change in size of a measurable lesion/s. Given that patients with NEPC do not often secrete PSA and all patients on study will have measurable disease, the primary outcome will be determined by radiologic response and progression. PSA response rate is a secondary endpoint.

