12.3.1 Change in lesion size

Complete response (CR) is defined as complete disappearance of all measurable and evaluable lesions by physical examination or imaging studies and normalization of PSA with no appearance of new lesions for > 1 month. Partial response (PR) is defined as a 30%

or greater reduction in the sum longest unidimensional diameter of all measurable lesions. There may be no new lesions. Stable Disease (SD) is characterized by patients who do not meet the criteria of PR and who are without signs of progressive disease for at least 1 month. Disease Progression (DP) is defined as a greater than 20% increase in the sum longest unidimensional diameters of the indicator lesions or the appearance of new lesions. Bone scan progression (evaluable disease only) is defined by PCWG2 criteria. Per consensus guidelines in CRPC, to be considered measurable, lymph nodes need to be at least 2 cm in greatest dimension and 1.5 cm in short axis. [32 and RECIST 1.1]

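### The only definition of rPFS leaves out death, so a Kaplan-Meier analysis that follows it censors deaths without documented progression and makes rPFS too favourable

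*Protocol*

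**What the plan says.** - **rPFS.** The protocol summary, under Secondary Endpoint(s), holds the only definition: "rPFS will be defined as the time from first treatment day until objective or symptomatic radiologic progression". The sentence just before it does name death, but for another endpoint: "Overall Survival is defined as time from first treatment until death".
- **Name.** The summary's secondary objectives call the endpoint radiographic progression free survival. Section 2.2 has "To determine the progression free survival with MLN8237" and gives no event definition.
- **Progression.** Section 12.3.1 states: "Disease Progression (DP) is defined as a greater than 20% increase in the sum longest unidimensional diameters of the indicator lesions". It adds new lesions, and bone scan progression by PCWG2. Death is not part of it.
- **Analysis.** The summary's analysis plan states: "For OS and rPFS, Kaplan-Meier survival analysis and 95% confidence intervals will be calculated using Greenwood's formulae". The parallel sentence in section 12 names OS only.
- **Primary endpoint.** Section 12.1 states: "The primary endpoint is the proportion of patients who are free from radiographic progression at 6 months following treatment with MLN8237". The summary and section 2.1 use similar wording, and none of the three says that the patient must be alive. Section 12.3 adds that "the primary outcome will be determined by radiologic response and progression".
- **Who is counted.** Section 12.1 requires 12 or more progression-free patients among the 48 entered, and plans 60 enrolled: "Assuming 10-20% of patients will be unevaluable/ineligible". Section 4.2 keeps all registered subjects in the intent-to-treat analysis. It allows replacement only of those who do not complete one planned cycle.

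**The concern.** A progression-free survival endpoint ordinarily fails at progression or death. Here the definition fixes progression alone as the event. In a Kaplan-Meier analysis, follow-up that ends without the defined event is censored, and censoring assumes that the patient remains at the same risk of later progression as those still followed. That is implausible for a patient who has died of advanced disease. The censoring is informative, and it flatters the curve.

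Such deaths are to be expected in some number. Section 1.1 says that most patients with NEPC survive less than one year. Scheduled scans come after every third 21-day cycle, so a death before about day 63 has no scheduled follow-up scan. The End of Study visit must fall more than 30 days after the last dose, so a patient who dies sooner does not reach it. Scans prompted by symptoms, which section 7.0 leaves to the investigator's discretion, and scans at progression will reduce the number but not to zero.

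What is at stake is a secondary estimate reported under a name that readers will take to include death. The primary endpoint does not say alive either, so its scoring of early deaths is worth stating.

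**Working it through.** **1. The plan's own design figures.** Inputs from section 12.1: n = 48, success if 12 or more, null 15%, alternative 30%. Exact binomial:

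- P(X ≥ 12 | 48, 0.15) = 0.048, within the 5% level.
- P(X ≥ 12 | 48, 0.30) = 0.819, above the 80% power.
- 48 / (1 − 0.20) = 60 enrolled.

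The stated design reproduces.

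**2. Effect on rPFS.** Let S be the true 6-month rPFS with death counted, and d the share of all patients whose first event by 6 months is a death without documented progression. The documents do not give d; 2%, 5% and 8% are assumptions (about 1, 2.4 and 3.8 of 48 patients). The share of first events that are such deaths is f = d / (1 − S). With proportional hazards for the two kinds of event, censoring the deaths gives an expected Kaplan-Meier value of S^(1 − f).

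For S = 0.15:

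| d | f = d / 0.85 | 0.15^(1 − f) |
|---|---|---|
| 2% | 0.024 | 15.7% |
| 5% | 0.059 | 16.8% |
| 8% | 0.094 | 17.9% |

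For S = 0.30, f = d / 0.70 = 0.029, 0.071 and 0.114, and 0.30^(1 − f) = 31.0%, 32.7% and 34.4%.

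The direction does not depend on d. Since f is at least 0 and S is below 1, S^(1 − f) is never below S.

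**3. Primary endpoint, if early deaths were dropped.** Suppose the true alive-and-progression-free share is 15%, and patients who die without documented progression are excluded or replaced so that 48 others are analysed. The success probability becomes p = 0.15 / (1 − d). With the same assumed d:

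| d | p | P(X ≥ 12 of 48) |
|---|---|---|
| 0 (deaths kept as failures) | 0.150 | 0.048 |
| 2% | 0.153 | 0.054 |
| 5% | 0.158 | 0.066 |
| 8% | 0.163 | 0.081 |

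This is an upper bound for each d. Section 4.2 limits replacement to patients who do not complete one planned cycle, and section 12.1 does not class deaths as unevaluable.

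**The case against.** **Censoring is inferred.** No section says that deaths are censored, event and censoring rules are often left to a statistical analysis plan, and the name of the endpoint suggests that death was meant to count. The name is fair evidence of intent. But the protocol does not leave the event open: it fixes it, and an analysis plan that counted deaths would have to override that definition. The word symptomatic does not help, since it still qualifies radiologic progression. Read literally, the definition describes time to progression under another name. The bias is relative to what the name promises.

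**Limited consequence.** rPFS is one of several secondary endpoints in a single-arm trial, with no test or decision rule attached. Eligibility requires an estimated life expectancy above 3 months, which should make very early deaths uncommon. Both points stand and hold the severity down.

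**A stronger reading of the primary endpoint.** A reader might infer that a patient who dies early without a progression scan counts as a success, which would inflate the false-positive rate of the main test. The documents do not support this. The rule counts patients free from progression at 6 months among the 48 entered, and a patient who has died is not naturally in that state. The intent-to-treat sentence in section 4.2 keeps all registered patients in the analysis. What remains is that no sentence states how an early death is scored.

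**Conclusion.** The point holds for rPFS. Its only definition omits death, contrary to its name, and the planned Kaplan-Meier analysis would then give an estimate equal to or above the intended one. The excess at 6 months is about 0.7, 1.8 or 2.9 percentage points on a true 15%, for an assumed 2%, 5% or 8% of patients dying without documented progression. The direction is certain. The size rests on those assumed shares and on proportional hazards, and cannot be settled from the protocol. Section 12 also fails to repeat the rPFS analysis given in the summary.

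For the primary endpoint the matter is one of clarification. The natural reading scores early deaths as failures. Even if they were excluded, the chance of a false positive would move only from 0.048 to 0.054, 0.066 or 0.081 for the same shares. Severity is minor to should-fix and rests on the rPFS definition.

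**What to change.** - Define rPFS in the summary as the time from first treatment to radiographic progression or death from any cause, whichever comes first. Put the definition and its Kaplan-Meier analysis into section 12, and align the objective in section 2.2.
- Word the primary endpoint in the summary and in sections 2.1 and 12.1 as alive and free from radiographic progression at 6 months, with earlier deaths kept in the denominator as failures.
- Confirm that the 15% and 30% benchmarks, which the protocol takes from a cited phase II trial, count deaths as events. If they do, N=48 and the cut-off of 12 are unchanged. If they do not, the hypotheses and the power need to be restated.

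The cost is a wording amendment. Death dates are already collected for OS, so no new data are needed. The downside is a slightly less favourable rPFS estimate.
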